## **I. OBJECTIVES**

---

Please note that this project is supported by a grant funded by the National Institute on Drug Abuse. The grant and protocol follow many the same procedures as our pilot study that has been approved for almost two years; "An Observational Study of Cannabidiol, Neurocognition, and Mood," and the protocol number is 14-0087 (e.g., having the participants purchase a strain from a local dispensary with some subjects being assigned

to less harmful strains that are lower in THC or higher in CBD). IRB approval of the protocol is needed to respond to the just-in-time request by January 2016.

Over the last several years, the United States has witnessed enormous changes concerning the acceptance of marijuana. Colorado, Washington, *Oregon, Alaska, and D.C.* have legalized recreational use of marijuana with several other states likely to follow in 2016. In the first four months of 2014 in Colorado, sales of marijuana exceeded \$200,000,000. In 2015, state officials expect demand in the legal market to exceed 130 metric tons. Considering the rapidly changing cultural, political, and legal landscape, the scientific literature that **should** inform public policy and harm reduction approaches is inadequate and outdated.

There are a number of critical limitations in the extant literature that must be addressed if scientists are to influence the regulation of marijuana. First and foremost, scientists need to understand the effects of commonly used marijuana strains, **as they are used in every day life**, as opposed to relying solely on testing the effects of government grown marijuana in controlled laboratory experiments. This information is critical for making recommendation about how to reduce the potential for harmful use of marijuana. For example, cannabidiol (CBD) appears to mitigate some of the effects of tetrahydrocannabinol (THC), and the ratio of CBD to THC may have a large impact on the effects of the marijuana, which in turn may have important implications for harm reduction. To that end, the overarching objective of this program of research is to advance a more nuanced understanding of the potential harm associated with different strains of marijuana, using a naturalistic design with high external validity, thereby avoiding many of the pitfalls and limitations of previous research. **To that end, regular marijuana users who normally use marijuana with a THC potency of ~18% will be asked to either continue to smoke or ingest normal marijuana or switch to a strain that is theoretically less harmful (i.e., has less THC and/or more CBD).** The information gained from this research will inform the public about the potential harms of different cannabinoids and strains. It may also have a translational application with respect to identifying THC levels or CBD:THC ratios that could be the focus of future regulatory actions.

1. The first specific aim will examine cannabis products that differ markedly on THC potency (low, medium, or high: i.e. 6%, 12%, 18% THC for smoked flower and low, medium, and high: i.e. ranging from less than 2.5mg to greater than 10mg THC for edibles) but do not differ on the potency of other major cannabinoids (< .5%) to determine whether the level of THC in the product is associated with increased intoxication and greater harmful effects using a naturalistic design.

- **Hypothesis 1.** Assuming that greater THC potency leads to greater levels of intoxication, it is hypothesized that individuals who receive the higher THC strains will demonstrate significantly greater blood THC levels. *Alternatively, it may be that individuals titrate their dose based on potency so that they achieve the same blood levels, in which case blood levels of THC should not differ between the strains.*
- **Hypothesis 2.** It is hypothesized that blood levels of THC will be positively associated with greater harm on a number of variables previously shown to be associated with THC, such as diminished working memory and increased drug reward.

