### **Is Greater THC Potency Associated with Greater Harm?**

Recent reviews have suggested that the greater potency of today's marijuana, compared to earlier decades, may lead to significantly greater levels of intoxication and harm (e.g., Volkow et al., 2014). However, only a few previous studies have actually examined the effect of marijuana potency on smoking topography and subjective and cognitive measures, and these studies are outdated. For example, an early study that compared the different potencies of marijuana (.36%, .73%, 1.45% THC) found that individuals who were given the lower potency marijuana smoked significantly more than individuals who smoked the high potency marijuana, suggesting that individuals may compensate for lower potency by simply smoking more (Cappell & Pliner, 1974). However, overall levels of subjective intoxication were still greater in the high potency group, indicating that individuals may smoke less but still experience greater harm with the higher potency marijuana. A subsequent study found no effect of potency on smoking topography (Perez-Reyes et al., 1982). A study published in the late 1980s used a more sophisticated approach to compare marijuana with three different potencies (0, 1.3%, 2.7% THC). Heishman et al. (1989) suggested that individuals significantly changed their smoking topography when receiving the higher potency marijuana, as evidenced by lower puffs and inhalation volumes. Others have also noted changes in topography, such that individuals who receive higher potency marijuana smoke less, even though there were still dose response effects (Kelly, Foltin, & Fischman, 1993). In sum, a handful of studies prior to 1993 suggest that individuals smoke less when they are smoking a higher potency strain, but may still experience greater intoxication and marijuana effects. As noted by Volkow et al. (2014), this literature is seriously limited by the potency of the marijuana used (usually 0 to 3.5%). The THC potency of marijuana in Colorado often exceeds 18%. Studies are desperately needed to examine these higher potency strains.

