### **Overview and Design of Study 1 (e.g., Aim 1, Hypotheses 1 and 2).**

Study 1 is designed to test the hypothesis that a high THC strain of marijuana will be associated with greater blood levels of THC and greater harmful effects, as compared to a lower THC strain, when used in a

naturalistic environment. To that end, regular flower marijuana users, who, according to our preliminary data, typically use marijuana with a THC potency of ~18%, will be assigned to use one of three strains with no CBD but with different THC potencies (low, medium, or high: e.g. 6%, 12%, or 18% THC for smoked flower) and regular edible marijuana users who typically purchase 10 mg products will be allowed to use as they normally would (producing naturally occurring low, medium, and high groups: e.g. less than 2.5mg to greater than 10 mg THC n=33 per group) for five days prior to participating in the experimental session. Measures will be collected at Appointment 1: (Baseline/**Session 1**), after 5 days of using the assigned strain, but in a sober condition before use in our mobile laboratory at Appointment 2: (**Session 2**), they will then return to their home to use the assigned strain and return to the mobile laboratory (**Session 3**), and 60 minutes after their last use at home (**Session 4**). Details regarding sample ascertainment, marijuana administration, timing of measures to be collected, power analyses, and the analytic plan for Study 1 follow. Thus, Study 1 will involve a 3 Cannabis strains: high, medium, and low THC x 4 (Time: 1, 2, 3, 4) mixed factorial design.

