### **Power Analysis and Sample Size Requirement for Hypotheses 1 and 2**

Sample size was selected to permit analysis of the primary research questions at two-tailed alpha of .05 and power level of .80. Estimates of effect size follow Cohen (1988) and were conducted in G\*Power 3 (Faul et al., 2007). The primary analysis is the test of the strain X time interaction effects across repeated assessments of THC in the blood as well as assessments of working memory and the rewarding effects of the marijuana. To be conservative, we thus estimated an ICC of .60. Using a mixed model ANOVA design, with three groups, four assessment points, and an average ICC = .6 between assessment points, a total n=99 (33 per group) will allow us to detect an interaction effect as small as  $f=.12$ .

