### **Effects of THC Potency on THC Blood Levels, Working Memory, and Reward**

The first aim is designed to test whether the “potency” of marijuana in terms of THC level in the plant translates directly to THC levels in the blood. To test **Hypothesis 1**, those individuals who receive the high THC strain will demonstrate significantly greater blood THC levels, we will utilize random coefficient regression (RCR; Cohen et al., 2013) via SAS Proc Mixed. The between subjects factor will be strain (high THC versus medium THC versus low THC) and the within subjects factor is time (Time 1, Time 2, Time 3, Time 4). Blood level of THC is the dependent measure. The test of the strain X time interaction will indicate whether the pattern of effects is such that blood levels increase to a greater degree and remain higher across the course of the study in the strains with higher THC. Thus, we expect both a significant interaction as well as a main effect of strain. Assuming a significant omnibus test of the interaction, we will decompose the interaction

via planned posthoc contrasts in order to understand at which time points the three strains are different. At Appointment 1, Time 1 (baseline) we do not expect differences in THC since none of the participants will have switched strains. Appointment 2, Time 2 is the sober, before use at Time 3. Thereafter, we expect a difference in THC at Appointment 2, Time 3 in the high THC versus the medium and low THC groups, and that while all groups will decrease in THC over the course of the laboratory appointment between Time 3 and 4, the high THC group will continue to show higher blood levels than the medium THC group, and the medium THC group will show higher blood levels than the low THC group. Note that we will include a quadratic effect in the multilevel model both to appropriately model the quadratic effect and whether that quadratic trend differs by condition. It is important to note that since we are not directly controlling administration, and have instructed participants to ingest the marijuana ad libitum, that they themselves may moderate their consumption to achieve “desired” THC levels, as our pilot data suggest. Thus, those in the low and medium THC group may ingest more in order to match their typically desired level, and thus the groups might converge. In this case, it is possible that we may see fewer difference in blood levels of THC, or non-significant differences at some timepoints across groups.

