**Hypothesis 2** tests whether blood levels of THC are positively associated with diminished working memory and greater rewarding effects of the marijuana, operationalized with the DEQ. If analyses of Hypothesis 1 show that there are main effects by group suggesting that the higher THC strain results in significantly higher THC levels in the blood than the medium or low THC strains, the between-groups variable for models testing Hypothesis 2 will be group and we will include all four time points. Since participants were randomly assigned to group, this test allows for the highest internal validity in terms of causal conclusions about the effects of THC. If, on the other hand, participants titrate their own use such that there are few reliable between-groups differences, then actual blood levels of THC will become the between-groups (continuous) independent variable in tests of Hypothesis 2 and we will utilize timepoints 3-4 as the within-subjects effect of time. Our preliminary studies confirm wide variability in THC levels even among individuals using the same strain, so there will be adequate between-participant variability for these analyses. In either case, we will again use the RCR approach described above, and standard approaches to the estimation of interactions in regression (Aiken & West, 1991) in the case of a continuous IV (i.e., mean-centering prior to creation of the interaction term). In each model, the predictors will include the group variable (or continuous THC blood levels), a time variable, and their interaction.

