The Pittsburgh Sleep Quality Index (PSQI)	
 
The Pittsburgh Sleep Quality Index (PSQI) is an effective instrument used to measure the quality and patterns of sleep. It differentiates “poor” from “good” sleep by measuring seven domains: subjective sleep quality, sleep latency, sleep duration, habitual sleep efficiency, sleep disturbances, use of sleep medication, and daytime dysfunction over the last month. The client self rates each of these seven areas of sleep
 
	
Cold Presser Task	
 
Participants immerse their hand in cold liquid and withdraw their hand from the liquid (pain tolerance) and the timing is recorded. There is a risk of discomfort.
 
	
Session 2 & 3		
Exercise Cognitions	
 
This measure will be used to examine the acute cognitive effects of cannabis consumption on participants’ exercise cognitions, specifically exercise intentions, motivation, and self-efficacy. These measures are slight variations of assessments of exercise cognitions used in our prior work (Bryan & Rocheleau, 2002).
 
	
Session 3 & 4		
The Drugs Effects Questionnaire (DEQ)	
 
The Drug Effects Questionnaire (DEQ) is a 5 items visual analog scale used to measure the strength of marijuana as well as the desirable effects (de Wit & Phillips, 2012).
 
	
The Addiction Research Center Inventory	
 
The Addiction Research Center Inventory (ARCI; Martin, Sloan, Sapira, & Jasinski, 1971), including the ARCI—Marijuana (M) scale (Chait, Fischman, & Schuster, 1985) will be used to measure subjective effects of marijuana in addition to drug-induced euphoria, stimulant-like effects, intellectual efficiency and energy, sedation, dysphoria, and other somatic effects.
 
	
Session 4		
Cold Presser Task		

 
Participants immerse their hand in
 
		

cold liquid and withdraw their hand from the liquid (pain tolerance) and the timing is recorded. There is a risk of discomfort.		
Assessment of Blind and Potency of Marijuana	
 
At the end of the experimental session, participants will be asked to guess which strain they received and to guess the potency of THC and CBD in that strain.
 
	

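### Aim 1 asks whether potency raises intoxication, but no model names intoxication as its outcome, and the one strain comparison of a subjective effect (the DEQ, as reward) is dropped if blood THC does not differ by strain

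*Protocol*

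**What the plan says.** Specific Aim 1 (Protocol, I. OBJECTIVES) compares products of differing THC potency "to determine whether the level of THC in the product is associated with increased intoxication and greater harmful effects using a naturalistic design". It therefore asks two things: does potency raise intoxication, and does it raise harm.

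Hypothesis 1, in the same section, opens with "Assuming that greater THC potency leads to greater levels of intoxication, it is hypothesized that individuals who receive the higher THC strains" and predicts higher blood THC in those participants. The analysis section on THC potency, blood levels, working memory and reward confirms: "Blood level of THC is the dependent measure". The overview of Study 1 describes what is tested as "greater blood levels of THC and greater harmful effects, as compared to a lower THC strain". Intoxication is not named there.

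The power section makes the strain-by-time interaction the primary analysis for blood THC "as well as assessments of working memory and the rewarding effects of the marijuana", with no condition attached. The Hypothesis 2 text specifies "greater rewarding effects of the marijuana, operationalized with the DEQ" and sets a branching rule. If Hypothesis 1 shows group differences in blood THC, group is the between-subjects factor and all four time points are used. If participants titrate and the groups differ little, measured blood THC replaces group and only time points 3 and 4 are used.

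In the measures table (XII. PROCEDURES), the DEQ is a five-item visual analogue scale covering drug strength as well as desirable effects. The Addiction Research Center Inventory (ARCI), with its Marijuana scale, "will be used to measure subjective effects of marijuana in addition to drug-induced euphoria". Both are scheduled at Sessions 3 and 4. The ARCI appears in no hypothesis, power statement or model.

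**The concern.** The first half of Aim 1 enters Hypothesis 1 as a premise, and the test is then of exposure. A higher blood level in the high-potency arm would show greater exposure, not greater intoxication.

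The branching rule makes this matter more. Suppose the arms do not separate on blood THC. The protocol treats that as a live possibility and says its pilot data point that way. Strain then leaves the model for the DEQ, and what remains is an association between self-selected blood THC and the DEQ. That association is observational and does not say whether potency changes how intoxicated people become. The protocol itself says the comparison by assigned group gives the strongest basis for causal conclusions. The rule gives up that comparison when the blood result has not settled the question, although scales that could address it are already collected.

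**Working it through.** **1. The plan's own figure.** Inputs from the power section: three groups, four assessments, ICC .6, f=.12, two-tailed alpha .05, N=99. For a within-between interaction, assuming sphericity:

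- λ = f²·N·m/(1−ρ) = .0144 × 99 × 4 / .4 = 14.26
- df = (3−1)(4−1) = 6 and (99−3)(4−1) = 288
- Power = .811. The smallest equal-group N for 80% power is 99.

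The stated sample size reproduces. Allowing 10% attrition, 33/.9 = 36.7, or 37 per group and 111 in total, as stated.

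**2. Outcome by outcome.**

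| Place in the protocol | Outcome | Comparison | Condition |
|---|---|---|---|
| Aim 1 | Intoxication; harm | Product THC level | None |
| Hypothesis 1 | Blood THC | Strain | None |
| Power section | Blood THC, working memory, reward | Strain × time | None |
| Hypothesis 2, groups differ in blood THC | Working memory, DEQ as reward | Strain | Hypothesis 1 positive |
| Hypothesis 2, titration | Working memory, DEQ as reward | Blood THC | Hypothesis 1 not positive |

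Intoxication appears in the first row and in no later one. Rows three and five conflict: the power section treats the strain comparison of reward as primary in all cases, and the Hypothesis 2 text withdraws it in one.

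**3. The DEQ has two assessments, not four.** It is scheduled at Sessions 3 and 4 only, so the first branch cannot use all four time points for it, and the four-assessment power figure does not carry over. With m=2: λ = .0144 × 99 × 2 / .4 = 7.13 on 2 and 96 df, which gives power .65 at f=.12. The smallest interaction detectable with 80% power is f=.142.

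**4. What an unconditional strain comparison could detect (illustration).** The inputs are 33 per arm, ICC .6, and the mean of Sessions 3 and 4. The effect size is my assumption: a 0.6 SD high-versus-low difference with the medium arm midway.

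- Variance of a two-session mean: (1+.6)/2 = .8 in single-session SD² units.
- High versus low: .6/√(2 × .8/33) = .6/.220 = 2.72. With 96 error df, power is .770.
- Three-arm test: λ = 33 × (.3² + 0 + .3²)/.8 = 7.43 on 2 and 96 df, power .668.
- High versus low reaches 80% power between 0.62 SD (.796) and 0.63 SD (.809).
- For the three-arm test the minimum detectable main effect is f=.283. With equal spacing f = d/√6, so d = .283 × 2.449 = 0.69 SD.

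The existing sample can support such a test for moderate to large differences.

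**The case against.** A reader might infer that no planned test compares subjective drug effect between strains. The protocol does not support that. The power section lists the strain comparison of reward as primary, the first branch of Hypothesis 2 compares the DEQ by group, and the DEQ covers drug strength. This stands, and it narrows the point. It does not remove it: the comparison is labelled reward, no strength score is separated out, and the second branch drops strain.

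A reader might also infer from the literature review that exposure can converge while intoxication still differs. The review cites an early study in which low-potency users smoked more and yet "overall levels of subjective intoxication were still greater in the high potency group". It reports no blood levels for that study, and the pattern is equally consistent with incomplete titration and higher exposure in the high-potency group, which Hypothesis 1 could detect. The passage gives a reason to measure intoxication. It does not show that blood THC fails as a marker.

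Third, using blood THC as an objective measure of dose is an open and reasoned choice, and the protocol nowhere says that equal blood levels would mean equal intoxication. Both are true. The choice supports blood THC as an exposure measure, but Aim 1 is worded in terms of intoxication.

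Finally, the harm variables are introduced as examples, and scoring of DEQ items or the role of the ARCI may be set in an analysis plan that is not shown. Leaving those details out is no defect. The point rests on what the protocol itself fixes: the premise in Hypothesis 1, its dependent measure, and a branching rule at odds with the power section.

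**Conclusion.** The point holds as a mismatch between Aim 1 and the tests, and as a conflict between the power section and the Hypothesis 2 rule. Under titration, the plan as written discards the randomised comparison of the only subjective-effect measure it assigns to a model, and the intoxication part of Aim 1 would then have no randomised test. If blood THC does differ by strain, the DEQ is compared by strain, but under the label of reward. The randomisation argument applies to flower users assigned a strain; edible users choose their own products.

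No stated figure is in error. The powers of .77 and .67 rest on an assumed 0.6 SD effect, equal spacing of the three arms, and the protocol's ICC applied to the two-session mean. They show that the test is feasible and do not measure a loss caused by the plan. This should be corrected, but it does not undermine the design.

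**What to change.** - Word Hypothesis 1 as a test of exposure, with blood THC as its outcome and without the premise about intoxication.
- Reconcile the Hypothesis 2 rule with the power section: run the strain comparison of subjective effects at Sessions 3 and 4 whatever the blood THC result, and keep the model with blood THC as predictor as an additional analysis.
- Name one already collected score, either the DEQ strength item or the ARCI-Marijuana score, as the intoxication outcome. Place it as key secondary and base the Aim 1 statement on intoxication on it.
- State that models for the DEQ or ARCI use two assessments.

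Both scales are already scheduled at these sessions, so no new data collection is needed and only analysis wording changes. The downside is one more tested endpoint, which needs its place in the multiplicity scheme.

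### Hypothesis 1 names equal blood THC through titration as its rival answer but tests only for differences, so a non-significant result cannot tell full titration from partial compensation

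*Protocol*

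**What the plan says.** The Objectives give Hypothesis 1 two answers. Either stronger strains produce higher blood THC, or users adjust their intake "so that they achieve the same blood levels, in which case blood levels of THC should not differ between the strains".

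The power section makes the first answer the tested one: "The primary analysis is the test of the strain X time interaction effects across repeated assessments of THC in the blood". The section on effects of THC potency repeats this. It specifies a mixed model with strain, time and their interaction, and expects a strain main effect as well. If the omnibus interaction is significant, "we will decompose the interaction" by contrasts that locate the sessions at which strains differ.

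The same section then turns to self-regulated intake. Low- and medium-potency users may consume more, the groups may converge, and "it is possible that we may see fewer difference in blood levels of THC, or non-significant differences at some timepoints across groups". Under Hypothesis 2, the alternative to a significant group effect is that "participants titrate their own use such that there are few reliable between-groups differences". In that case measured blood THC replaces randomised group as the predictor.

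The background section on potency and harm summarises the earlier studies differently: users smoked less of stronger material but may still have been more intoxicated. That is incomplete compensation.

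**The concern.** Equal blood levels is an equivalence claim. Failing to reject a null of no difference does not establish it, because a true difference of moderate size can also go undetected. The protocol states no margin, no confidence-interval criterion and no measure of the degree of compensation. When differences are absent, the only reading it offers is titration.

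Partial compensation, in which blood THC rises with potency but less than proportionally, has no place in this two-way reading. Chance would help decide which side such a result falls on. Whether users titrate potency away is central to Aim 1, and the significance summary says the results may inform potency targets for regulation.

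**Working it through.** **Inputs from the protocol.** Two-tailed alpha .05 and power .80; three groups, four assessments, ICC .6; N = 99 (33 per group); detectable interaction f = .12 (power section). Flower potencies are 6%, 12% and 18% (section on administration at home).

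**Assumptions, not in the protocol.** Blood THC is analysed on the log scale with SD σ of 0.8, 1.0 or 1.2 (0.6 and 1.5 as sensitivity values). Blood THC is proportional to potency^(1−c), where c is the degree of compensation. Strain effects are equal at Times 3 and 4 and absent at Times 1 and 2. There are 33 randomised flower users per group.

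**1. The stated power.** λ = f²·N·m/(1−ρ) = .0144 × 99 × 4 / .4 = 14.26, with 6 and 288 df. Power is .811, so the stated sample size reproduces.

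**2. True ratios.** With c = 0, high:low is 18/6 = 3 and high:medium is 18/12 = 1.5. With c = 0.5, high:low is √3 = 1.73. With c = 1 all ratios are 1.

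**3. Omnibus interaction.** The centred log potencies are −0.597, 0.096 and 0.501, with sum of squares 0.617. With effects at two of four sessions, the squared interaction terms also sum to 0.617(1−c)². Hence λ = 33 × 0.617(1−c)² / (.4σ²), which is 50.9/σ² at c = 0 and 12.73/σ² at c = 0.5.

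**4. Single-session contrasts.** Noncentral t with 64 df and noncentrality (ln ratio/σ)·√(33/2).

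Probability of a non-significant result:

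| Scenario and test | σ = 0.8 | σ = 1.0 | σ = 1.2 |
|---|---|---|---|
| Half compensation, omnibus interaction | 7% | 24% | 43% |
| Half compensation, high v low | 22% | 41% | 55% |
| No compensation, omnibus interaction | <0.001% | 0.003% | 0.2% |
| No compensation, high v low | <0.1% | 0.7% | 4.4% |
| No compensation, high v medium alone | 47% | 63% | 73% |

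At σ = 0.6 the omnibus test misses half compensation only 0.2% of the time. At σ = 1.5 it misses half compensation 63% of the time and no compensation about 4%.

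**5. Precision.** At σ = 1.0 the 95% CI on a pairwise ratio extends a factor of 1.64 each way. An estimate just short of significance is about 1.64, so its upper limit is about 1.64² = 2.7, close to the 3 expected for high:low without compensation.

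**6. What a slope would deliver.** Regressing log blood THC at one session on log potency gives SE = σ/√(33 × 0.617) = σ/4.51, or .177, .222 and .266. Under full titration (true slope 0), the upper 95% limit falls below 1 in more than 99.9%, 99.4% and 96% of trials. For a purely illustrative two-sided margin of ±0.5 on the slope, the chance that the whole 95% CI lies inside is roughly 2Φ(0.5/SE − 1.96) − 1, which is 61%, 23% and 0%. These SEs take no credit for adjusting for pre-use THC or for combining Times 3 and 4.

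**The case against.** A reader might infer that a trial with no compensation at all would be read as titration. The table does not support that. The omnibus interaction comes first in the plan and would almost always be significant. Only the 18% v 12% contrast, taken alone, is often missed, and it would normally be read beside a significant omnibus test and a significant high-low contrast.

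A reader might also infer that the protocol commits itself to reporting a null as titration. It does not. The Objectives state only the valid direction, from titration to no difference, and the convergence passage is hedged throughout. The nearest thing to an operative rule is in the Hypothesis 2 paragraph, where it selects a predictor.

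It can further be said that the plan foresees fewer differences, that mixed-model contrasts yield estimates and intervals anyway, and that margins are commonly left to an SAP, which is not at hand. The absence of a margin alone would indeed be no finding. What stands is in the written text: sameness is a named answer, only difference tests are given, and the Hypothesis 2 branch equates titration with few reliable differences and changes the analysis on that basis.

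Finally, the SD, the log scale and the proportionality to potency are all assumed, and the miss rates depend heavily on the SD. That is correct, and it limits how firmly the size can be stated. The protocol itself reports wide variability in THC levels among users of the same strain.

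**Conclusion.** The concern holds in a limited form. The difference test for higher blood THC is sound and its power figure reproduces. The rival answer has no valid test, and non-significance cannot separate full titration from partial compensation. With half compensation, the planned omnibus test would be non-significant in about 7% to 43% of trials at log SD 0.8 to 1.2, and the single-session high-low contrast in 22% to 55%. If the log SD is as low as 0.6, the omnibus problem is negligible (0.2%). The logical gap remains at any SD, because a difference test cannot establish equality.

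These figures assume 33 randomised flower users per arm. The design overview gives n=33 per group within its description of the edible users, who are not assigned a strain, so the flower number per arm is uncertain. With fewer, the miss rates would be higher.

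**What to change.** Keep the strain by time interaction test for the claim of higher blood THC. In the analysis section for Hypothesis 1, restricted to randomised flower participants, add the slope of log post-use blood THC (Times 3 and 4) on log labelled potency with its 95% CI. A slope of 0 means full titration and 1 means no compensation, assuming blood THC is proportional to dose. Then state three rules:

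- Conclude that there is some titration only if the upper limit is below 1.
- Conclude that levels are the same only if the whole interval lies within a two-sided margin that the sponsor sets and justifies in advance. A one-sided limit would let over-compensation pass as sameness.
- Otherwise report the result as inconclusive.

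Add to the Hypothesis 1 and Hypothesis 2 paragraphs that a non-significant strain or strain by time test is not evidence of titration.

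The cost is a few sentences and one further model on data already collected. The drawback is that the claim of same levels will often be inconclusive at this sample size, as step 6 of the working shows. For comparison, a conventional equivalence test of the high:low ratio (two one-sided 5% tests) against a 1.73-fold margin would need 57 per group for 80% power at log SD 1.0. The protocol should also state the number of randomised flower users per arm.
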